5.5 PREMATURE TERMINATION OR SUSPENSION OF STUDY

This study may be temporarily suspended or prematurely terminated if there is sufficient reasonable cause. Written notification, documenting the reason for study suspension or termination, will be provided by the suspending or terminating party to <investigator, funding agency, the IND/IDE sponsor and regulatory authorities>. If the study is prematurely terminated or suspended, the PI will promptly inform the IRB and will provide the reason(s) for the termination or suspension.

Circumstances that may warrant termination or suspension include, but are not limited to:

- Determination of unexpected, significant, or unacceptable risk to participants
- Insufficient compliance to protocol requirements
- Data that are not sufficiently complete and/or evaluable
- Determination of futility

Study may resume once concerns about safety, protocol compliance, data quality are addressed and

satisfy the sponsor, IRB and/or FDA.

6 STUDY AGENT

6.1 STUDY AGENT(S) AND CONTROL DESCRIPTION

The following are the study drugs being used in this trial:

1. CC-122:

Celgene will supply CC-122 as capsules for oral administration in 0.5, 1, (both of these dose formulations are are encapsulated in size 3 capsule shells) and 2 mg (encapsulated in size 1 capsule shell) strengths. Each pinkish brown capsule shell contains microcrystalline cellulose, mannitol, crospovidone, colloidal silicon dioxide, and stearic acid.

Drug Safety Contact Information:

2. Nivolumab:

Commercial supply of nivolumab will be used in this study. This will be obtained through the Moffitt Cancer Center pharmacy.

6.1.1 DOSING AND ADMINISTRATION

CC-122 will initially be administered orally once daily (QD) on 5 consecutive days each week (5 days on, 2 days off). The starting dose will be 2 mg with dose adjustments for toxicity per the following table. Each cycle of treatment will be 28 days. The daily dose of CC-122 should be taken in the morning at least 1 hour before or 2 hours after a meal (breakfast) with a glass of water. CC-122 may be taken up to 12 hours late if dosing has been delayed on a single day; otherwise that day's dose should be omitted. A study diary will be maintained to assess compliance with drug therapy.

The following table outlines the dose reduction levels permitted on this study for CC-122. If a patient is unable to tolerate CC-122 at the 1mg dose, this drug will be permanently discontinued. The patient will be permitted to continue nivolumab as clinically appropriate.

CC-122 Dose; 5 days on, 2 days		
Starting Dose	2 mg	
1 st Dose Reduction	1.5 mg	
2 nd Dose Reduction	1 mg	

Nivolumab is given by intravenous infusion at a flat dose of 240mg on days 1 and 15 in a 28-day treatment

cycle. While regulatory approval for dosing at 480mg IV every 28 days was also recently obtained, we will maintain the approved biweekly dosing schedule in this trial based on the safety data from Study CC-122-HC-002 in hepatocellular carcinoma. Dose administration of +/- 2 days is permissible and will not constitute a deviation. There will be no dose adjustments for nivolumab. Please refer to the OPDIVO Package Insert (November-2018) for full prescribing information.

6.1.2 DURATION OF THERAPY

In the absence of progression or intolerable toxicity, therapy will continue up to a maximum of 52 weeks (13 cycles). For those patients who demonstrate continued improvement in radiographic response at scheduled restaging (anticipated around week 48) performed prior to reaching this landmark will be given the option of continuation of therapy. This provision is based on the recently reported analysis of advanced melanoma patients who achieved a complete response to pembrolizumab on KEYNOTE-001 where the median time to achieve CR was 12 months (range, 3-36).⁴⁴ For these subjects, therapy will continue for 1 cycle beyond CR (should they achieve this) or until 2 consecutive staging studies demonstrate a plateau in response. For those patients achieving CR as best response prior to 52 weeks, therapy can be discontinued provided they have completed at least 26 weeks of treatment.

If either CC-122 or nivolumab require discontinuation due to toxicity attributed exclusively to that agent (e.g., neutropenia secondary to CC-122), the second drug can continue for the duration as outlined above.

6.1.3 DOSE MODIFICATIONS

Dose delay criteria apply for all drug-related adverse events regardless of whether or not the event is attributed to nivolumab, CC-122, or both unless it is explicitly clear that the toxicity is exclusive to one drug alone. All study drugs must be delayed until treatment can resume, unless in the judgement of the clinical investigator (with discussion with the PI), there is compelling evidence to continue one of the agents without the other.

Causality should be assessed and provided individually for each study drug (CC-122 and nivolumab) for every AE/SAE based on currently available information. Causality is to be reassessed and provided as additional information becomes available.

6.1.3.1 CC-122 Dose Delay and/or Modifications:

The criteria for dose reduction and/or interruption for **non-hematological toxicities attributed to CC-122** are listed in the following table. Chronic Grade 2 toxicity attributed to CC-122 may warrant dose reduction of CC-122. If necessary, the PI may reach out to the appropriate medical personnel at Celgene to discuss this further.

Toxicity	Action		
Any Grade 4 including LFT elevation (exceptions include lymphopenia, asymptomatic amylase and lipase)	Discontinue CC-122		
Grade 3 or 4 clinical liver failure	Discontinue CC-122		

If recurrence of Grade 3 event after dose-reduction	Reduce dose to the next lower dose level; if available – If none available, CC-122 should be discontinued.
If recurrence of Grade 4 event after dose reduction	Discontinue CC-122
Any non-hematological toxicity requiring interruption for > 4 weeks	Discontinue CC-122
Troponin-T/I > ULN with associated significant elevation in BNP or with cardiac symptoms or significant changes in ECG or LVEF ¹	 Hold CC-122 Consider cardiology evaluation Follow troponin-T/I, BNP, and ECG at least every 7 days If troponin-T/I returns to normal levels in ≤ 7 days and there are no other significant cardiac findings, resume CC-122 at the next lower dose level If troponin T/I level elevation persists > 7 days, or recurs upon re-challenge, discontinue CC-122
Rash ≥ Grade 3	 If Grade 3 hold CC-122 until recovery to grade ≤ 1; if AE resolution to Grade ≤ 1 occurs ≤ 8 days, reintroduce CC-122 at the same dose level If AE resolution to Grade ≤ 2 or > 7 days, reintroduce CC122 on lower level, if available Discontinue CC-122 for 2nd occurrence of ≥ Grade 3 rash For desquamating (blistering) Grade 3 or any Grade 4 rash, discontinue CC-122 For maculopapular, aceiform, or pustular rashes lasting ≤ 7 days medical management is warranted including topical corticosteroids, anti-pruritic agents (if indicated). If this does not improve, oral steroids may be used. It is likely that this intervention will be utilized given the overlap of this toxicity with nivolumab (see appendix D)
Peripheral Neuropathy (neuropathies which begin or worsen while on study) ≥ Grade 3	 Hold CC-122 When the toxicity resolves to ≤ Grade 2 or to baseline, restart CC-122 at the next lower dose level
Allergic Reaction or Hypersensitivity ≥ Grade 3	Discontinue CC-122

Venous Thrombosis / Embolism (VTE) ≥ Grade 2; anticoagulation indicated	Hold CC-122 and start anticoagulation; restart CC-122 (maintain dose level) once therapeutic anticoagulation achieved AND it is clinically appropriate to resume. ²
Pneumonitis / Interstitial Lung Disease ³	 Grade 1: continue CC-122 Grade 2: interrupt CC-122; can resume at one dose level lower once ≤ grade 1 AND steroid taper completed. If recurrent Grade 2 toxicity on rechallenge, permanently discontinue CC-122 ≥ Grade 3: permanently discontinue CC-122
Other Grade 3 ⁴	 Hold one or both study drugs (based on attribution) When the toxicity resolves to < Grade 2, restart CC-122 at the next lower dose level

- 1. For BNP, greater than 20% increase from baseline value is considered significant. Any new ST segment or T wave changes, new bundle branch block, or new atrial or ventricular arrhythmia while on treatment with CC-122 is considered clinically significant. An absolute decrease in LVEF of > 10% from baseline (even if asymptomatic), or a decrease of estimated LVEF to ≤ 45% would mandate holding further CC-122 for up to 4 weeks. If improved LVEF (repeated 2-4 weeks after holding drug) to baseline value, resume CC-122 at next lower dose level, if available. If the decrease in LVEF is ≥ 20% (absolute decrease) from baseline or there is any evidence of symptomatic congestive heart failure, CC-122 will be permanently discontinued.
- 2. There are no prospective data available on the need to interrupt immunomodulatory agents like thalidomide, lenalidomide, CC-122 at the time of diagnosis of the VTE event. However as these drugs are prothrombotic, it is reasonable to hold CC-122 till therapeutic anticoagulation is achieved. For anticoagulants that do not require monitoring (such as low molecular weight heparin), CC-122 will be restarted 7 days after the initial hold. For drugs requiring monitoring (unfractionated heparin, warfarin), CC-122 will be resumed once the aPTT or INR are in the recommended therapeutic range for that individual agent, but no sooner than 7 days from the hold. Prior to resuming CC-122, clinically significant symptoms or signs related to VTE (e.g., chest pain, dyspnea, etc.) should have resolved. Persistence of leg/arm swelling (in case of DVT) would not be a contra-indication to resume therapy.
- 3. As pneumonitis is an expected toxicity with nivolumab, it may be difficult to ascertain the causality to one specific drug in this combination. The management algorithm to be followed based on the grade of toxicity is outlined in Appendix D.
- 4. Exceptions to this include lymphopenia, asymptomatic elevation in amylase or lipase, and isolated electrolyte imbalances/abnormalities that are not associated with clinical sequelae. Isolated electrolyte aberrations (e.g., sodium, potassium, magnesium, etc.) may require appropriate exogenous supplementation, but repeat levels must meet criteria outlined in the table to resume therapy.

Guidelines for hematological toxicity attributed to CC-122:

Toxicity	Action			
Grade 2 thrombocytopenia	No action			
Grade 3 thrombocytopenia	Hold until resolution to Grade 221			
	Follow CBC at least every 7 days			
	If resolution to Grade ②1 occurs ≤ 8 days, reintroduce CC-122 at the same dose level			
	If AE resolution occurs > 8 days, or event occurs within the same cycle, reintroduce CC-122 at the lower dose level, if available			
Grade 4 thrombocytopenia	Hold CC-122 until recovery to Grade 271			
	Follow CBC at least every 7 days			
	 Reintroduce CC-122 at the lower dose level, if available 			
Grade 3 neutropenia	Hold until resolution to Grade ≤ 1			
	Follow CBC at least every 7 days			
	 If AE resolution to Grade ≤ 1 occurs ≤ 8 days, reintroduce CC-122 at the same dose level 			
	 If AE resolution occurs > 8 days, or event occurs within the same cycle, reintroduce CC-122 at one dose level lower, if available 			
Grade 4 neutropenia	Grade 4: Hold CC-122 until recovery to Grade ???1.			
	Follow CBC at least every 7 days			
	 Reintroduce CC-122 at the lower dose level, if available 			
	 Use of growth factors (G-CSF, GM-CSF) is permitted at the discretion of the Investigator* 			
Febrile neutropenia	Hold further dosing until recovery to Grade ≤ 1 then resume dosing at one dose level lower, if available			
	Use of growth factors (G-CSF, GM-CSF) is permitted at the discretion of the Investigator*			

Any hematological toxicity requiring	Discontinue CC-122
interruption for > 3 weeks	

*The use of myeloid growth factors (filgastrim, sargramostin, peg-filgastrim, or biosimilars), if considered should be in accordance with the 2015 American Society of Clinical Oncology guidelines for the use of WBC growth factors. This includes use in subjects with neutropenia and fever who are at high risk for infection-related complications. These high-risk features are sepsis, age > 65 years, pneumonia, invasive fungal infection, other clinically documented infections, profound neutropenia (< 0.1×10^9 /L) and hospitalization at the time of neutropenia. The growth factor should be continued until the absolute neutrophil count (ANC) has improved to \leq grade 1 (equal to or greater than 1.5 $\times 10^9$ /L). If resumption of CC-122 in planned at a lower dose (if available), growth factors should have been discontinued at least 48 hours prior with reconfirmation of acceptable ANC on the day of planned resumption of treatment.

Additional toxicity-related precautions with CC-122:

CC-122 absorbs ultraviolet (UV) light between the frequencies of 290 and 700 nm and has been shown to distribute to the skin and eyes in nonclinical animal studies. As a precautionary measure, it is recommended that subjects avoid prolonged exposure to UV light, wear protective clothing and sunglasses, and use UV-blocking topical preparations while taking CC-122. This is outlined in the informed consent document.

6.1.3.2 Nivolumab Dose Delays and/or Modifications:

Nivolumab administration should be delayed for the following:

- Grade 2 non-skin, drug-related adverse event, with the exception of fatigue
- Grade 2 drug-related creatinine, AST, ALT and/or Total Bilirubin abnormalities
- Grade 3 skin, drug-related adverse event
- Grade 3 drug-related laboratory abnormality, with the following exceptions:
 - Grade 3 lymphopenia or asymptomatic amylase or lipase does not require dose delay
 - Grade 3 AST, ALT, Total Bilirubin will require dose discontinuation
- Any adverse event, laboratory abnormality, or inter-current illness, which in the judgment of the investigator warrants delaying the dose of study medication.

Participants who require delay of study drug administration should be re-evaluated weekly or more frequently if clinically indicated and resume dosing when re-treatment criteria are met.

Criteria to Resume Treatment with Nivolumab:

Participants may resume treatment with study drug when the drug-related AE(s) resolve to Grade \leq 1 or baseline value, with the following exceptions:

- Participants may resume treatment in the presence of Grade 2 fatigue
- Participants who have not experienced a Grade 3 drug-related skin AE may resume treatment in the presence of Grade 2 skin toxicity
- For participants with Grade 2 AST, ALT and/or Total Bilirubin Abnormalities, dosing may resume when laboratory values return to baseline and management with corticosteroids, if needed, is complete.
- Participants with combined Grade 2 AST/ALT AND total bilirubin values meeting discontinuation parameters should have treatment permanently discontinued.
- Drug-related pulmonary toxicity, diarrhea or colitis must have resolved to baseline before treatment is resumed. Participants with persistent Grade 1 pneumonitis after completion of a steroid taper over at least 1 month may be eligible for retreatment if they are asymptomatic and with normal pulse oximetry

readings in the absence of oxygen supplementation.

Participants with drug-related endocrinopathies adequately controlled with only physiologic hormone replacement may resume treatment provided any symptoms attributed to this event have improved to baseline. If the criteria to resume treatment are met, the participant should restart treatment at the next scheduled time point per protocol. However, if the treatment is withheld past the window period of the next scheduled time point per protocol to ensure adequate recovery from the adverse event or tapering of immunosuppression, the next scheduled time point will be delayed until dosing resumes. If treatment is withheld > 6 weeks from the last dose, the participant must be permanently discontinued from study therapy.

Treatment with Nivolumab should be **permanently discontinued** for the following:

- Any Grade 2 drug-related uveitis, eye pain or blurred vision that does not respond to topical therapy and does not improve to Grade 1 severity within the re-treatment period OR requires systemic treatment
- Any Grade 3 non-skin, drug-related adverse event lasting > 7 days, or recurs with the following exceptions for laboratory abnormalities, diarrhea, colitis, neurologic toxicity, drug-related uveitis, pneumonitis, bronchospasm, hypersensitivity reactions, infusion reactions, and endocrinopathies:
- Grade 3 drug-related diarrhea, colitis, neurologic toxicity, uveitis, pneumonitis, bronchospasm, hypersensitivity reaction, or infusion reaction of any duration requires discontinuation
- Grade 3 drug-related endocrinopathies, adequately controlled with only physiologic hormone replacement do not require discontinuation. Adrenal insufficiency requires discontinuation regardless of control with hormone replacement.
- Grade 3 drug-related laboratory abnormalities do not require treatment discontinuation except:
 - ◆ Grade 3 drug-related thrombocytopenia > 7 days or associated with bleeding requires discontinuation
 - ♦ Any drug-related liver function test (LFT) abnormality that meets the following criteria require discontinuation:
 - o Grade 3 drug-related AST, ALT or Total Bilirubin requires discontinuation
 - Concurrent AST or ALT > 3 x ULN and total bilirubin > 2x ULN
- Any Grade 4 drug-related adverse event or laboratory abnormality (including but not limited to creatinine, AST, ALT, or Total Bilirubin), except for the following events which do not require discontinuation:
 - Grade 4 neutropenia < 7 days
 - Grade 4 lymphopenia or leukopenia or asymptomatic amylase or lipase
 - Isolated Grade 4 electrolyte imbalances/abnormalities that are not associated with clinical sequelae and are corrected with supplementation/appropriate management within 72 hours of their onset
 - Grade 4 drug-related endocrinopathy adverse events, such as, hyper- or hypothyroidism, or glucose intolerance, which resolve or are adequately controlled with physiologic hormone replacement (corticosteroids, thyroid hormones) or glucose-controlling agents, respectively, may not require discontinuation of nivolumab.
- Any event that leads to delay in dosing lasting > 6 weeks from the previous dose requires discontinuation, with the following exceptions:
 - Dosing delays to allow for prolonged steroid tapers to manage drug-related adverse events are allowed.

The algorithms for management of immune toxicity attributed to nivolumab will follow recommendations outlined in the OPDIVO package insert and labeling information (November-2018) plus generally accepted guidelines for clinical care of IO toxicity management. These guidelines are summarized in Appendix D.

Tumor assessments should continue as per protocol even if dosing is delayed. Periodic study visits to assess safety and laboratory studies should also continue every 6 weeks or more frequently if clinically indicated during such dosing delays.

Treatment of Nivolumab Related Infusion Reactions:

Since nivolumab contains only human immunoglobulin protein sequences, it is unlikely to be immunogenic and induce infusion or hypersensitivity reactions. However, if such a reaction were to occur, it might manifest with fever, chills, rigors, headache, rash, pruritis, arthralgias, hypo- or hypertension, bronchospasm, or other symptoms. Infusion reactions should be graded according to National Cancer Institute Common Terminology Criteria for Adverse Events (NCI CTCAE [version 5.0]) guidelines.

Treatment recommendations are provided below and may be modified based on local treatment standards and guidelines as appropriate:

For Grade 1 symptoms: (Mild reaction; infusion interruption not indicated; intervention not indicated)

Remain at bedside and monitor participant until recovery from symptoms. The following prophylactic premedications are recommended for future infusions: diphenhydramine 50 mg (or equivalent) and/or paracetamol 325 to 1000 mg (acetaminophen) at least 30 minutes before additional nivolumab administrations.

For Grade 2 symptoms: (Moderate reaction requires therapy or infusion interruption but responds promptly to symptomatic treatment [eg, antihistamines, non-steroidal anti- inflammatory drugs, narcotics, corticosteroids, bronchodilators, IV fluids]; prophylactic medications indicated for <224 hours).

Stop the nivolumab infusion, begin an IV infusion of normal saline, and treat the participant with diphenhydramine 50 mg IV (or equivalent) and/or paracetamol 325 to 1000 mg (acetaminophen); remain at bedside and monitor participant until resolution of symptoms. Corticosteroid or bronchodilator therapy may also be administered as appropriate. If the infusion is interrupted, then restart the infusion at 50% of the original infusion rate when symptoms resolve; if no further complications ensue after 30 minutes, the rate may be increased to 100% of the original infusion rate. Monitor participant closely. If symptoms recur then no further nivolumab will be administered at that visit. Administer diphenhydramine 50 mg IV, and remain at bedside and monitor the participant until resolution of symptoms. The amount of study drug infused must be recorded on the electronic case report form (eCRF). The following prophylactic premedications are recommended for future infusions: diphenhydramine 50 mg (or equivalent) and/or paracetamol 325 to 1000 mg (acetaminophen) should be administered at least 30 minutes before additional nivolumab administrations. If necessary, corticosteroids (recommended dose: up to 25 mg of IV hydrocortisone or equivalent) may be used.

For Grade 3 or Grade 4 symptoms: (Severe reaction, Grade 3: prolonged [ie, not rapidly responsive to symptomatic medication and/or brief interruption of infusion]; recurrence of symptoms following initial improvement; hospitalization indicated for other clinical sequelae [eg, renal impairment, pulmonary infiltrates]). Grade 4: (life threatening; pressor or ventilatory support indicated).

Immediately discontinue infusion of nivolumab. Begin an IV infusion of normal saline, and treat the

participant as follows. Recommend bronchodilators, epinephrine 0.2 to 1 mg of a 1:1,000 solution for subcutaneous administration or 0.1 to 0.25 mg of a 1:10,000 solution injected slowly for IV administration, and/or diphenhydramine 50 mg IV with methylprednisolone 100 mg IV (or equivalent), as needed. Participant should be monitored until the investigator is comfortable that the symptoms will not recur. Nivolumab will be permanently discontinued. Investigators should follow their institutional guidelines for the treatment of anaphylaxis. Remain at bedside and monitor participant until recovery from symptoms. In the case of late-occurring hypersensitivity symptoms (eg, appearance of a localized or generalized pruritis within 1 week after treatment), symptomatic treatment may be given (eg, oral antihistamine, or corticosteroids).

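### Section 6.1.3.1 gives opposite CC-122 instructions for Grade 4 VTE and Grade 4 neuropathy and does not say which row governs

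*Combined protocol and SAP*

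**What the plan says.** All the main provisions sit in one table, the non-hematological table of section 6.1.3.1, which applies to toxicity attributed to CC-122.

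- **General Grade 4 row.** The trigger is "Any Grade 4 including LFT elevation (exceptions include lymphopenia, asymptomatic amylase and lipase" and the action is to discontinue CC-122.
- **VTE row.** The trigger is Grade 2 or higher with anticoagulation indicated. The action is "Hold CC-122 and start anticoagulation; restart CC-122 (maintain dose level) once therapeutic anticoagulation achieved AND it is clinically appropriate to resume".
- **Footnote 2, attached to the VTE row.** It gives the reason for the hold: "However as these drugs are prothrombotic, it is reasonable to hold CC-122 till therapeutic anticoagulation is achieved". For anticoagulants that need no monitoring, "CC-122 will be restarted 7 days after the initial hold". For monitored agents, restart waits for the therapeutic range and at least 7 days. Clinically significant VTE symptoms must have resolved. No grade limit is set.
- **Neuropathy row.** The trigger is Grade 3 or higher. CC-122 is held, then: "When the toxicity resolves to ≤ Grade 2 or to baseline, restart CC-122 at the next lower dose level".
- **Time limit.** "Any non-hematological toxicity requiring interruption for > 4 weeks" leads to discontinuation.
- **Recurrence row.** "If recurrence of Grade 4 event after dose reduction" leads to discontinuation.

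In section 10.3, under the stopping rules for excessive toxicity, a DLT is the discontinuation of either or both drugs because of toxicity.

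**The concern.** A Grade 4 VTE or Grade 4 neuropathy attributed to CC-122 meets two triggers in the same table. One action ends CC-122 permanently and the other leads to a restart. An investigator facing a life-threatening clot can therefore point to a row that stops the drug and to a row that resumes it at full dose, although the protocol itself describes the class as prothrombotic.

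Patient safety is the main stake. The second is consistent counting: because a DLT is defined by discontinuation, the row chosen can decide whether the patient enters the toxicity count.

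**Working it through.** No figure in the plan is in dispute, so the check compares the rows and then sizes the difference for one patient.

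**1. Do both triggers include Grade 4?** Yes. The VTE and neuropathy rows have a lower grade bound and no upper one. The general row covers any Grade 4 event and names only lymphopenia and asymptomatic amylase and lipase as exceptions.

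**2. Does any text set precedence?** None was found in the introduction to 6.1.3, in the table, or in its four footnotes. There are only indirect signs:

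- The residual Grade 3 row is labelled as covering *other* Grade 3 events, so it yields to the specific rows. The Grade 4 row is labelled *any*. This contrast leans toward the Grade 4 row governing.
- Six event rows have a grade range that reaches Grade 4: liver failure, rash, allergic reaction, pneumonitis, VTE and neuropathy. (The troponin row carries no grade and is not counted.) The first four all stop CC-122 at Grade 4. The rash row says so expressly: "For desquamating (blistering) Grade 3 or any Grade 4 rash, discontinue CC-122". Only VTE and neuropathy do not, and nothing says whether that is deliberate.
- The recurrence row has two readings. It may presuppose that some Grade 4 events are dose-reduced, or it may mean a toxicity reduced at a lower grade that returns at Grade 4. It is not used as evidence here.

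**3. Size for one patient.** Dose levels are 2, 1.5 and 1 mg, given 5 days in 7 (section 6.1.1). Weekly dose = daily dose × 5.

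| Dose at event | General Grade 4 row | VTE row (same dose) | Neuropathy row (next lower) |
|---|---|---|---|
| 2 mg | 0 | 2 × 5 = 10 mg/week | 1.5 × 5 = 7.5 mg/week |
| 1.5 mg | 0 | 1.5 × 5 = 7.5 mg/week | 1 × 5 = 5 mg/week |
| 1 mg | 0 | 1 × 5 = 5 mg/week | no lower level: 0 |

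The VTE restart can fall between day 7 of the hold (footnote 2) and day 4 × 7 = 28 (four-week limit). The neuropathy conflict arises only if recovery comes within 28 days and the patient is on 2 or 1.5 mg. At 1 mg the rows agree.

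**4. DLT status.** If the event is attributed to CC-122 alone, the general row makes it a DLT. The specific row does not, unless CC-122 is stopped for toxicity later. If nivolumab is also implicated, section 6.1.3.2 stops nivolumab for Grade 4 drug-related events outside its listed exceptions, so the patient is a DLT under either row.

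**5. Minor items.**

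- *Grade 3 rash.* Recovery to Grade 1 or better within 8 days restarts the same dose, while recovery after more than 7 days restarts a lower dose. Both conditions hold when 7 < d ≤ 8, that is, on day 8. The difference is one level: (2 − 1.5)/2 = 25%, or (1.5 − 1)/1.5 = 33.3%. The row also holds the drug until Grade 1 or better, yet provides for a lower-dose restart at Grade 2.
- *Nivolumab six-week limit.* In 6.1.3.2, the criteria to resume treatment require permanent discontinuation from study therapy after a hold of more than 6 weeks, with no exception. The permanent-discontinuation list in the same subsection exempts prolonged steroid tapers.

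**The case against.** The strongest reply is that the text already favours one answer. The Grade 4 row says *any*, names its exceptions, and contrasts with a Grade 3 row that expressly yields. For VTE, one action also satisfies both rows: restart depends on clinical appropriateness, so an investigator who stops CC-122 breaches neither. Other safeguards exist. VTE symptoms must resolve, section 5.4.1 lets the investigator end participation in the patient's interest, the trial is single-center, and section 8.4.2 provides continuous monitoring with weekly group review.

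Much of this stands. The lean toward discontinuation is real, the VTE restart is a conditional permission, and the safeguards reduce the risk. They do not remove the contradiction. Footnote 2 is phrased as a direction to restart and has no grade cap. The neuropathy row has no clinical-appropriateness condition, so a patient who recovers in time is sent to restart by one row and to stop by the other. The list of exceptions in the Grade 4 row is introduced in open-ended terms, which leaves room to argue that a specific row is a further exception. A single center can still treat two patients differently.

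The rash item is a one-day timing overlap plus an unclear restart grade, and the six-week item is a missing exception in one of two places. Both are minor.

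**Conclusion.** The table is wrong as written for Grade 4 VTE and Grade 4 neuropathy attributed to CC-122: two stated rules give opposite actions and none takes precedence. The difference for a patient is 5 to 10 mg/week of CC-122 against none after VTE, and 5 or 7.5 mg/week against none after neuropathy. It can also change one patient's DLT status when CC-122 alone is blamed. The conclusion rests only on the table wording and needs no assumed event rate.

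Three stronger readings are tempting and are not supported:

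- *The toxicity boundary is compromised.* The documents give no rate of Grade 4 VTE or neuropathy, so no change in the DLT rate or in the chance of stopping can be derived. An exact recursion through the printed cohort 1 boundary gives a 24.8% crossing probability at a true DLT rate of 25%, in line with the stated maximum of 25%. The sample sizes and response rules are untouched.
- *The protocol compels a restart after a life-threatening clot.* It does not, because clinical appropriateness, symptom resolution and investigator judgement all intervene.
- *The recurrence row shows that dose reduction after Grade 4 was intended.* It can equally describe a lower-grade event that returns at Grade 4.

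The point deserves correction because it concerns safety and costs little to settle.

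**What to change.** **Main change.** Limit the VTE row and footnote 2 to Grade 2-3 and the neuropathy row to Grade 3, so that Grade 4 discontinues CC-122. If the sponsor intends rechallenge after either event, name it as an exception in the general Grade 4 row instead. That clinical choice is the sponsor's.

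**Minor changes.**

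- For Grade 3 rash, use one cut-off (8 days or less against more than 8 days, as in the Grade 3 neutropenia row), and have the sponsor state a single restart grade. Removing the Grade 2 restart would be a clinical change and should be made openly.
- Add the steroid-taper exception to the six-week sentence in the criteria to resume nivolumab.

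**Cost.** A protocol wording amendment, with no added patients, visits or tests. The downside of capping the rows is that any patient with one of these Grade 4 events loses the option of CC-122 rechallenge and counts as a DLT.
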